2.1.3 Sample Size Consideration

The sample size was selected based on prior experience to ensure that the safety, tolerability and PK/PD relationships will be adequately assessed while minimizing unnecessary patient exposure. There is no statistical rationale for the selected sample size.

2.1.4 Planned Interim Analysis

No interim analysis is planned. However, during the study, an unblinded primary database lock analysis may be conducted after all patients complete the treatment period to assess the safety and PK/PD, and exploratory efficacy of the results. The analysis will be executed with controlled dissemination to ensure the integrity of ongoing data collection while maintaining sufficient blinding in the study. All the post-baseline coagulation panel data and unblinded interim analysis will be conducted by unblinded team members including a clinician and biostatistician who will not be associated with the direct conduct of the study after the unblinding occurs with interim analysis. The individuals involved in the unblinded interim analysis will be identified and documented at the time of unblinded interim analysis according to Ionis SOP.

The Investigator, study staff, patients, blinded monitors, and members of the Sponsor's clinical operations team and data management team will remain blinded throughout the study.

2.1.5 Incomplete or Missing Data

In general, missing data values will not be imputed. Incomplete data handling rules will be described in the specified section if needed.

2.2 Demographic and Baseline Characteristics

Demographic and Baseline characteristics (including dialysis and ESRD disease characteristics e.g., age, gender, ethnicity, race, weight, height, BMI, Primary Cause of ESRD, Time Since the Start Date for Renal Replacement Therapy (First Ever)/ESRD First Transplant or First Dialysis Ever, Time since the Start Date for Hemodialysis (Most Recent)) obtained before the first study drug administration will be summarized using descriptive statistics by treatment group and all patients for ITT population, Safety Population.

Additional summaries will be provided for each substudy if there are adequate number of patients enrolled.

Age for each patient is defined as number of years between informed consent date and birth date.

For summarizing race, if multiple races are recorded in the database, then 'Multiple Race' is used in the summary table.

The study sample sizes will be summarized by trial unit (site) for enrolled patients. All patients with signed informed consent will be included in the enrolled patients.

Dialysis prescription characteristics (Days of the week dialysis is scheduled, prescribed number of sessions, prescribed duration, dry weight total, type of dialyzer to be used, type of vascular access, Location of Arteriovenous Fistula/Graft and Location of Catheter) will be summarized for ITT population, Safety Population. Additional summaries will be provided for each substudy population if there are adequate number of patients enrolled.

Medical history will be coded by Medical Dictionary for Regulatory Activities (MedDRA) Version 21.0. Medical history will be summarized by System Organ Class (SOC) and Preferred Term (PT). In addition, the frequency and percentage of patients with CHAOS score (0, 1, 2, ..., 6) will be provided for AF substudy population. The CHADS score is the total of the scores per the risk criteria below with data collected from Targeted Medical History CRF.

Score	CHADS2 Risk Criteria
1 point	Congestive heart failure
1 point	Hypertension
1 point	Age 75 years
1 point	Diabetes mellitus
2 points	Stroke/transient ischemic attack

Patient randomization and disposition will be summarized by treatment group and all patients. All patients enrolled will be included in the summary. The summaries will include: the total number of patients were screened, randomized, dosed and included in each population, the number of patients completed treatment, the primary reason for terminating treatment, the number of patients completed post-treatment evaluation period, and the primary reason for terminating post-treatment evaluation period.

In addition, the disposition will be summarized by treatment group and all patients for AF substudy population, PK substudy population, and Platelets Function/Activation substudy population.

All protocol deviations will be listed. Protocol deviations will also be summarized by region, trial unit, and treatment group.

2.3 Safety Analyses

Safety analyses will be based on the safety population. Safety summary tables will be presented by treatment group and ISIS 416858 total.

2.3.1 *Exposure*

Treatment duration, time on study, number of doses and amount and total volume of Study Drug (ISIS 416858 or placebo) received will be summarized by treatment group and ISIS 416858 total.

The treatment duration (days) for each patient is defined as last dose date - first dose date +1.

The time on study will be defined as the total number of days a patient is known to be followed on study calculated as follows:

$$\text{Time on study} = \text{Last date on study} - \text{Date of first dose} + 1.$$

Where the last date on study is defined as the date of the latest visit with evaluation, or time of death from all available data for a given patient. Visits with refused or unable to contact are not visits with evaluation.

The amount of Study Drug received (mg) for each patient is defined as the total volume (mL) administered from the 200 mg/mL stock solution.

2.3.2 *Compliance*

Percentage of compliance will be calculated and summarized by treatment groups and ISIS 416858 total.

$$\text{Study drug compliance} = 100 \times (\text{Total number of doses with injections given} / \text{Total number of doses with injections expected}).$$

If a patient discontinued the study treatment, the total number of doses with injections expected is counted, per the schedule of injections, up to the last attended study visit during the treatment period.

2.3.3 *Adverse Events*

The treatment emergent adverse events (TEAE) are defined as those AEs that occurred after dosing and those existing pre-dose AEs that worsened post-dose during the study.

The most conservative approach will be used to determine if the event occurs during the treatment or follow-up periods:

- AEs that have onset dates or resolution dates prior to the first study treatment dates will be considered to have occurred prior to the study period. If the onset or resolution date

of an AE is a partial date with only month or year available or complete missing, then the event is assumed to be within the study period unless the year is prior to the year of the first study treatment date, or if in the same year, the month is prior to the month of the first study treatment date.

- AEs that have onset dates after study termination date for the post-treatment evaluation period will be assumed to have occurred after the study period. If the onset of an AE is a partial date with only month or year available or complete missing, then similar approach as above will be used

The ESRD related adverse event is defined as TEAE with "Related", "Possible" relationship to ESRD. If the AE relationship to ESRD is missing or it has been defined as "Unlikely/remote", it will be considered as a Non-ESRD/Procedure-related AE.

All adverse event summaries will be restricted to treatment-emergent adverse events (TEAE).

The incidence of treatment-emergent adverse events will be summarized by treatment group and ISIS 416858 total, by MedDRA preferred term and system organ class for the followings:

- AE Overview
- AE Overview for ESRD/Procedure-related adverse events
- AE Overview for non-ESRD/Procedure-related adverse events
- TEAEs
- TEAE for ESRD/Procedure-related adverse events
- TEAE for non-ESRD/Procedure-related adverse events
- TEAEs potentially related to study drug. Potentially related is defined as "Related", "Possible", or missing relationship to study drug
- Serious TEAEs
- Serious TEAEs potentially related to study drug
- TEAEs resulting in permanently discontinuation of study drug
- Subjects with non-serious AE. The subjects with non-serious AE are those subjects having at least one non-serious adverse event, but no SAE.
- TEAE by maximum severity. At each level of patient summarization, a patient is classified according to the highest severity if the patient reported one or more events. Adverse events with missing severity will categorized as "Missing" for this summary. Event counts will also be provided for each level of severity.
- TEAEs potentially related to study drug by maximum severity

- Serious TEAEs potentially related to study drug by maximum severity

Events will be sorted by total incidence of each System Organ Class then by total incidence of each Preferred Term within each System Organ Class. For incidence counts, each patient will be counted only once within each Preferred Term and within each SOC. Percentages will be based on the number of patients in a particular treatment arm.

2.3.3 .J Local Cutaneous Reactions at the Injection Site

Local cutaneous reaction at injection site (LCRJS) is defined as (A) moderate or severe Injection Site Erythema, Swelling, Pruritus, Pain or Tenderness that started on the day of injection, persisted for at least two days; or (B) any AE at the Study Drug injection site, regardless of severity, that leads to discontinuation of study drug, where AE at the Study Drug injection site is the principal reason for discontinuation.

LCRIS will be summarized using the MedDRA coding system, by preferred term. Patients with moderate, severe and any LCRIS will also be summarized. Discontinuations due to AE at the injection site will be summarized separately.

Percentage of injections leading to LCRIS will be summarized by preferred terms and overall using the descriptive statistics. Additionally, percentage of Study Drug injections leading to LCRIS will be summarized by the moderate, severe severity and overall discontinuation of study drug due to AE at Study Drug injection site.

Percentage of Study Drug injections leading to LCRIS will be calculated as follows for each subject: (A/B)*100, where A=number of Study Drug injections with a LCRIS, and B=total number of Study Drug injections. Doses that are split across multiple Study Drug injections are counted as a single injection.

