3.4 Overall Study Duration and Follow-up

For all cohorts, the Study will consist of a 4-week screening period for procedures after the informed consent is signed. An additional 21 days is permitted prior to screening period for signing of the informed consent. All cohorts will consist of a 26-week Treatment Period, and a 12-week Post-Treatment Evaluation Period. For all cohorts, please refer to the Schedule of Procedures in [Appendix A](#).

Subjects may be required to attend additional visits for monitoring of adverse events (AE) or abnormal investigation results. The frequency of additional monitoring will be determined by the Investigator in consultation with the Sponsor.

If Study Drug is discontinued for any reason, subjects are encouraged to continue their regular assessments for the duration of the treatment period and post-treatment evaluation period, unless subject informed consent is withdrawn.

3.4.1 *Screening*

After signing the informed consent form, subject eligibility for the study will be determined within 4 weeks prior to Study Day 1.

During the screening period, at Study Days S-14 (\pm 3) and S-7 (\pm 3), subjects should receive 2 noncontiguous SC injections of 0.75 mL saline. As with Study Drug, these may be administered immediately after dialysis is completed when blood is returning to the subject but must be within 2 hours after dialysis (within 15 minutes is preferred) to determine tolerability to SC injections.

All women will have a serum pregnancy test done between Study Days S-28 and S-14 that must be resulted prior to dosing on Study Day 1.

All screening lab re-tests should be resulted by the central lab prior to randomization on Study Day 1.

3.4.2 *Treatment*

Eligible subjects will receive study treatment every week for 26 weeks. The treatment period consists of the period from the first Study Drug (ISIS 416858 or placebo) injection to the last injection on Day 176 (Week 26), or early study termination.

3.4.3 *Post-Treatment*

Subjects will have follow-up evaluation visits on Study Week 27 (PK Subgroup only), and for Study Weeks 28, 30, 32, 34, 36, 38 (all subjects), or early study termination. The final study visit will be Study Day 260.

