Baseline for the routine clinical assessments of chemistry and hematology, PD markers, assessment of clotting, PK assessments, vital signs and ECG for the study will be the time-point prior to the first administration of Study Drug and prior to dialysis on Day 1 ([Appendix A](#)). If Day 1 values are not available, screening values will be used. For Urea Reduction Ratio, the blood collections for blood urea nitrogen (BUN) prior to dialysis as well as the post-dialysis sample on Day 1 will be used.

6.1.3 *Treatment Period (Day 1 to Day 176)*

Enrolled subjects may be administered ISIS 416858 or placebo immediately after dialysis is completed (when blood is returning to the subject) but must be within 2 hours (preferably within 15 minutes) approximately once each week for a total of 26 weeks of treatment.

Once-weekly SC administration will occur during Weeks 1 to 26 (Days 1, 8, 15, 22, 29, 36, 43, 50, 57, 64, 71, 78, 85, 92, 99, 106, 113, 120, 127, 134, 141, 148, 155, 162, 169, and 176).

For Study Drug administration on Study Day 1, no dosing window is allowed. For Weeks 2 to 26, a \pm 3-day window may be utilized but Study Drug should be administered each week. Study Drug doses should be administered at least 72 hours apart.

Additionally, no dose of Study Drug will be administered before reviewing a valid platelet result. Valid platelet counts must be conducted every 2 weeks and reviewed prior to dosing. If the platelet result is unavailable (e.g., due to hemolysis, clumping, etc.) from the central lab, a repeat local lab will be conducted and reviewed prior to dosing.

Any questions on study procedures and visit windows may be directed to the Sponsor (or designee).

During all subject contacts, Investigators will check for and record:

- Bleeding events
- AEs
- Concomitant medication changes

Safety and clinical laboratory evaluations as well as PD markers, assessment of clotting, blood sampling, including those for routine PK as well as PK substudy analysis will be performed as indicated in [Appendices A, B, and C](#). Subjects participating in the platelet substudy will have additional blood sampling and processing on Study Days 1, 78, and 176 during the Treatment Period.

Any AEs, including bleeding events, will be recorded. This may include additional information regarding events of interest (i.e., thrombotic events).

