8.3 Other Protocol-Required Treatment Procedures

Subjects are required to be receiving in center hemodialysis at least 3 times a week for a minimum of 9 hours per week while receiving Study Drng during the treatment period. Subjects no longer receiving the required in center hemodialysis should continue in the study with the regularly scheduled assessments, but will no longer receive Study Drng.

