8.6 Stopping Rules for Study Drug

When stopping rules are met for liver chemistry elevations, platelet count reductions, or bleeding events, then Study Drug administration must be discontinued. However, subjects are encouraged to continue with study assessments through the treatment and post-treatment evaluation periods, but will no longer receive Study Drug.

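### The compliance denominator for subjects who stop study drug runs to their last attended treatment-period visit, so the percentage mixes dosing adherence with study retention.

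*Combined protocol and SAP*

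**What the plan says.** SAP 2.3.2 defines compliance as 100 times doses given over the "Total number of doses with injections expected", summarized by treatment group and for the pooled active group. For a subject who discontinued treatment, expected doses are counted "per the schedule of injections, up to the last attended study visit during the treatment period".

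The protocol keeps stopping drug separate from leaving the study:

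- Section 3.4: "If Study Drug is discontinued for any reason, subjects are encouraged to continue their regular assessments for the duration of the treatment period", and likewise for the post-treatment period.
- Section 3.4.2: the treatment period runs from the first "injection to the last injection on Day 176 (Week 26), or early study termination". An individual's early stop of drug does not end it.
- Section 8.6, on stopping rules: "subjects are encouraged to continue with study assessments through the treatment and post-treatment evaluation periods, but will no longer receive Study Drug".
- Section 8.3: subjects off the required hemodialysis "should continue in the study with the regularly scheduled assessments, but will no longer receive" study drug.
- Section 8.7 repeats the encouragement to stay on study after discontinuation.

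Dosing is "approximately once each week for a total of 26 weeks of treatment" (protocol 6.1.3), with the 26 dosing days listed there.

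**The concern.** The cut-off for expected doses is visit attendance, not the end of dosing. A subject who stops drug and then does what the protocol asks keeps adding expected doses that cannot be given. Two subjects with the same dosing record can therefore have very different compliance, depending only on whether they stayed in follow-up.

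What is at stake is whether the compliance table can be interpreted. A low value may mean missed injections, or it may mean an early stop in a subject who was retained. If stops or retention differ between arms, the comparison of compliance between doses and placebo mixes three things: adherence, discontinuation and retention.

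**Working it through.** **Reproducing the plan's own count.** The documents state no compliance figure, but the full denominator can be checked. Protocol 6.1.3 lists 26 dosing days (Day 1, then every 7 days to Day 176). Protocol Table 3 gives total doses for completed treatment: 5200/200 = 26, 6500/250 = 26 and 7800/300 = 26. The two sources agree.

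**Formula under SAP 2.3.2.** Compliance = 100 × (doses given) / (scheduled dosing days up to the last attended treatment-period visit).

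**Single subjects.** The documents do not say when subjects stop. Assume a stop after 4 to 24 doses, with every scheduled dose taken until then:

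| Doses given, then stopped | Leaves at last dose | Last visit 1 week later | Last visit 4 weeks later | Stays to Day 176 |
|---|---|---|---|---|
| 4 | 4/4 = 100% | 4/5 = 80.0% | 4/8 = 50.0% | 4/26 = 15.4% |
| 8 | 8/8 = 100% | 8/9 = 88.9% | 8/12 = 66.7% | 8/26 = 30.8% |
| 12 | 12/12 = 100% | 12/13 = 92.3% | 12/16 = 75.0% | 12/26 = 46.2% |
| 16 | 16/16 = 100% | 16/17 = 94.1% | 16/20 = 80.0% | 16/26 = 61.5% |
| 20 | 20/20 = 100% | 20/21 = 95.2% | 20/24 = 83.3% | 20/26 = 76.9% |
| 24 | 24/24 = 100% | 24/25 = 96.0% | 24/26 = 92.3% | 24/26 = 92.3% |

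Dosing is the same across each row; only attendance changes. In the last row, four weeks later would pass Day 176, so the count is capped at 26.

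**Arm means.** The documents give no stop or retention rates, so these are assumptions: 20% of active and 10% of placebo subjects stop after 12 doses, and everyone else scores 97%.

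- All stoppers stay to Day 176 (46.2% each): active 0.8 × 97 + 0.2 × 46.2 = 86.8; placebo 0.9 × 97 + 0.1 × 46.2 = 91.9. Placebo is 5.1 points higher.
- Half stay (stopper mean (46.2 + 100)/2 = 73.1%): active 77.6 + 14.6 = 92.2; placebo 87.3 + 7.3 = 94.6. Placebo is 2.4 points higher.
- None stay (100% each): active 77.6 + 20 = 97.6; placebo 87.3 + 10 = 97.3. Active is 0.3 points higher.
- With 30% against 15% stopping and all staying: 0.7 × 97 + 0.3 × 46.2 = 81.7 against 0.85 × 97 + 0.15 × 46.2 = 89.4, a gap of 7.6 points.
- With equal stop rates, timing and retention in both arms the gap is zero.

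**After the change.** Ending the count at discontinuation gives every stopper in these examples 100%, whether or not they stay. The 20% against 10% case then gives 97.6 against 97.3 at any retention rate.

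**Can another reading rescue the text?** If the treatment period ended at a subject's own last dose, the problem would vanish. Protocol 3.4 rules that out, because it asks subjects already off drug to continue for the duration of that period.

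**The case against.** The strongest reply is that little depends on this number. SAP 2.3.2 only calculates and summarizes compliance; no test, model or endpoint uses it. The per-protocol set (SAP 2.1.2, protocol 10.3) counts missed doses and does not use the percentage. Early stopping is also visible elsewhere: SAP 2.3.1 reports treatment duration and number of doses, the disposition summary gives reasons for ending treatment, SAP 2.3.3 tabulates adverse events leading to permanent discontinuation, and SAP 2.3.4 lists patients meeting stopping rules. All of this stands. It limits the consequence, but it does not make the percentage mean what its name says.

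A second reply is that ending the count at discontinuation has its own flaw: someone who chooses to stop after 3 doses would score 3/3 = 100%, like a completer. That is true, and it is why the share of planned doses (here 3/26 = 11.5%) must be shown alongside.

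Four stronger readings are tempting, and the documents do not support them:

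- A reader might infer that the tolerability comparison is distorted. Tolerability is assessed through adverse events, laboratory tests, vital signs and similar measures, not through compliance.
- A reader might expect a spurious gap of 5 to 8 points between arms. That needs twice as many stops on active drug and every stopper staying to Day 176, whereas staying is mostly only encouraged. The scenarios above run from about zero to 7.6 points.
- A reader might treat every stop after bleeding as required. Protocol 8.6 makes discontinuation mandatory when a bleeding stopping rule is met, while 8.6.3 says dosing may be stopped and allows for resumption. Those sections must be reconciled.
- A reader might assume the discontinuation date is already captured. Protocol 8.7 requires the reason in the eCRF; the documents do not confirm that the date is there.

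**Conclusion.** The concern holds as a defect in one descriptive measure. The rule as written makes compliance depend on retention, and nothing else in the documents repairs it. For one subject with full dosing until the stop, staying to Day 176 lowers the score from 100% to 15.4% after 4 doses, 30.8% after 8 and 92.3% after 24. These figures rest only on the 26-dose schedule and the assumed time of stopping.

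The effect on arm means cannot be fixed from the documents; it depends on how many stop, when, and how many stay. No test or analysis population changes. The change is worth making because the rule is explicit, the resulting figure cannot be interpreted for retained stoppers, and the repair is cheap.

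**What to change.** In SAP 2.3.2, count expected doses per the injection schedule from the first dose up to permanent discontinuation of study drug, or up to Day 176 if drug was not discontinued. Use the recorded discontinuation date if it is collected. If it is not, state a derivation that still counts doses missed before the decision to stop. The last dose date alone would not do this: a subject who takes 8 doses, misses 3 and then stops would score 8/8 = 100%, against 8/11 = 72.7% when the missed doses are counted.

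Beside it, report by arm the percentage of the 26 planned doses received, with 26 as the denominator for every subject, so that voluntary early stoppers do not look like completers.

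Separately, reconcile protocol 8.6 and 8.6.3 on whether a bleeding event requires a stop.

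The compliance change costs one sentence in the SAP, one extra summary row and possibly a derived date. It needs no change to the conduct of the trial.

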2.2 Therapeutic Rationale

Approximately 2 million individuals receive dialysis for end-stage renal disease (ESRD) globally and this number is increasing rapidly as both the incidence of ESRD rises and access to dialysis as a life sustaining therapy increases (Caskey et al. 2011). Dialysis patients are at high risk of thrombotic events due to their high degree of comorbid conditions and because they have a hypercoagulable state. This hypercoagulable state appears to be driven by widely used drugs (e.g., erythropoiesis stimulating agents), inflammation and endothelial dysfunction from uremia, and contact between blood and the extracorporeal circuit. The hypercoagulable state results in clinically meaningful negative outcomes. The risk of stroke in dialysis patients may be 10-times higher than the general population (Sood et al. 2009). Dialysis patients have a 5-fold higher risk of myocardial infarction than the general population and even moderate chronic kidney disease alone is considered the risk equivalent of diabetes mellitus for cardiovascular thrombotic events (Go et al. 2004; Tonelli et al. 2012). Furthermore, dialysis patients depend on patent vascular access to receive hemodialysis. Dialysis patients have a high chance, approximately 10% chance per year of having their vascular access compromised by thrombosis resulting in a potentially life-threatening situation requiring urgent intervention (Jean-Baptiste et al. 2008; Schild et al. 2008). Finally, dialysis patients are hospitalized an average of 3 times per year and are at high risk of VTE (Tveit et al. 2002). Despite this high risk of VTE, there remains considerable uncertainty as to the benefit-to-risk ratio of VTE prophylaxis. This is of particular importance when considering the optimal treatment for ESRD, renal transplantation, in which VTE can compromise the ability to receive a transplant, the function of an already transplanted kidney,

and/or the life expectancy of a patient who recently received a transplant (i.e., post-operative VTE) (Irish 2004).

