9.3 Definitions

9.3.1 *Adverse Event*

An adverse event (AE) can be any unfavorable and unintended sign (including an abnormal laboratory finding), symptom, or disease temporally associated with the use of a medicinal (investigational) product, whether or not the AE is considered related to the medicinal (investigational) product.

Adverse events are to be identified between study visits by evaluating components of the medical record that contain valid and verifiable claims about a medically untoward event. For hemodialysis subjects, this includes a complete review of changes in the dialysis prescription in the dialysis chart orders section or information provided to the study staff directly by the subject. Dialysis treatment summaries (rnn-sheets) should be reviewed for pertinent information when indicated.

9.3.2 *Adverse Drug Reaction and Unexpected Adverse Drug Reaction*

All noxious and unintended responses to a medicinal product related to any dose should be considered adverse drug reactions (ADR).

An unexpected ADR is any ADR, the nature or severity of which is not consistent with the applicable product information, e.g., Investigator's Brochure for an unapproved medicinal (investigational) product.

9.3.3 *Serious Adverse Event (SAE)*

A SAE is any AE that in the view of either the Investigator or Sponsor, meets any of the following criteria:

- Results in death
- Is life threatening: that is, poses an immediate risk of death at the time of the event
An AE or suspected adverse reaction is considered "life-threatening" if, in the view of either the Investigator or Sponsor, its occurrence places the subject at immediate risk of death. It does not include an AE or suspected adverse reaction that, had it occurred in a more severe form, might have caused death
- Requires inpatient hospitalization or prolongation of existing hospitalization
Hospitalization is defined as an admission of greater than 24 hours to a medical facility and does not always qualify as an AE
- Results in a persistent or significant incapacity or substantial disruption of the ability to conduct normal life functions

- Results in a congenital anomaly or birth defect in the offspring of the subject (whether the subject is male or female)

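### The non-serious AE table drops every subject who had an SAE but divides by the whole arm, so it understates non-serious AEs, and more so in an arm with more SAEs

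*Combined protocol and SAP*

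**What the plan says.** SAP 2.3.3 lists the AE tables to be produced by treatment group, preferred term and system organ class. One is for subjects with non-serious AEs, and the same bullet defines these as subjects "having at least one non-serious adverse event, but no SAE". On the denominator the section says: "Percentages will be based on the number of patients in a particular treatment arm". No other denominator is given for this table.

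The setting is fixed by nearby text. "Safety analyses will be based on the safety population", and SAP 2.3.3 limits all AE summaries to treatment-emergent events. I therefore read the SAE in the definition as a serious TEAE. Follow-up is long: protocol 3.4.3 says "The final study visit will be Study Day 260", so an SAE in either the 26-week treatment period or the 12-week post-treatment period removes the subject.

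The same list also plans tables of all TEAEs, serious TEAEs and TEAEs by maximum severity. None of them gives non-serious TEAEs for all subjects.

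**The concern.** A reader will take the table as the incidence of non-serious AEs. Its numerator instead leaves out every subject who also had an SAE, related to study drug or not, while those subjects stay in the denominator. The restriction acts on subjects, not events, so an unrelated SAE late in follow-up removes a subject's earlier non-serious events under every term.

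Two features of this trial make that relevant. Protocol 9.3.4 treats both serious and non-serious major and clinically relevant non-major bleeds as events of interest, so a subject with one serious bleed and several non-serious bleeds disappears from the non-serious table. Protocol 9.4.3.5 allows a non-serious AE to end as having become serious; that generates an SAE and removes the subject.

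What is at stake is the comparison between doses and placebo. If a dose produces more SAEs, its non-serious table is depleted more, and the dose can look better tolerated on this table for that reason alone.

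**Working it through.** **Inputs from the documents.** The numerator and denominator rules are in SAP 2.3.3. Arm sizes follow from about 204 subjects in three equal cohorts randomised 3:1: 204/3 = 68; 68 × 3/4 = 51 on each active dose; 3 × 17 = 51 on pooled placebo. The documents give no figure for this table and no expected SAE or non-serious AE rate for the trial, so there is nothing to reproduce. Every rate below is an assumption unless marked otherwise.

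**Step 1: the overall line, with no modelling.** A subject with a TEAE and no SAE must have had a non-serious TEAE. So overall

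row = (subjects with any TEAE) − (subjects with a serious TEAE).

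Both counts are already planned, so this line adds nothing, and it falls one for one as SAEs rise. Illustration with assumed rates: any TEAE 95% in both arms, SAEs 40% versus 55%. The row prints 95 − 40 = 55% versus 95 − 55 = 40%.

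**Step 2: a single preferred term.** Let T be the number of subjects with the term, S the number with a serious event of that term, and N the number with a non-serious event of it. Then T − S ≤ N ≤ T. A subject in the row has the term and no SAE at all, so row ≤ T − S ≤ N. The printed count can never exceed the true one. It falls short whenever a subject has a non-serious event of the term and an SAE of any kind.

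**Step 3: size.** Let p be the true proportion with a non-serious AE and q the proportion of the arm with an SAE. Under independence the table prints p(1 − q), so the understatement is 1/(1 − q):

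| q (assumed) | factor |
|---|---|
| 20% | 1.25 |
| 30% | 1.43 |
| 50% | 2.0 |
| two-thirds | 3.0 |

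Positive association makes it larger. If 95% of subjects with an SAE and 70% of those without have a non-serious AE, q = 50% gives a true 0.95 × 0.5 + 0.70 × 0.5 = 82.5% against a printed 0.70 × 0.5 = 35%, a factor of 2.4.

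**Step 4: between arms.** Take p = 80% in both arms, n = 51 each, q = 40% versus 55%, independence. Printed: 0.80 × 0.60 = 48% versus 0.80 × 0.45 = 36%, about 24 versus 18 subjects. The 12-point gap is spurious; the unrestricted count gives 80% in both.

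**Step 5: what the one background figure can support.** Protocol 2.2 says "dialysis patients are hospitalized an average of 3 times per year", and protocol 9.3.3 makes an AE serious if it "Requires inpatient hospitalization or prolongation of existing hospitalization". Over 260 days the mean is 3 × 260/365.25 = 2.14 admissions. The factor is 1/P(0), where P(0) is the chance of no SAE, using Poisson or negative binomial counts with dispersion k (a smaller k means more clustering):

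| Share of admissions that are SAEs (assumed) | Poisson | k = 1 | k = 0.5 |
|---|---|---|---|
| all | 8.5 | 3.1 | 2.3 |
| three-quarters | 5.0 | 2.6 | 2.1 |
| half | 2.9 | 2.1 | 1.8 |
| a quarter | 1.7 | 1.5 | 1.4 |

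If enrolled patients instead have 1 to 1.5 admissions a year, all SAEs, then k = 1 or 0.5 gives P(0) of 0.48 to 0.64, a factor of about 1.6 to 2.1.

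**The case against.** **The row is openly defined.** The SAP states the exclusion in the same bullet, and the proportion is correct for that mutually exclusive category. This stands as far as it goes: the percentage would not be miscalculated. But the short title invites the ordinary reading, and the SAP supplies no table for that reading.

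**Other tables carry the events.** This also stands in part. Non-serious events of subjects with an SAE remain in the all-TEAE and maximum-severity tables, and the serious-TEAE table allows the bounds in Step 2. Injection-site reactions, flu-like reactions and minor bleeding are summarised separately (SAP 2.3.3.1 to 2.3.3.3) without an SAE exclusion. No event is lost from reporting. Bounds are not the count, however, and severity is not seriousness.

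**The consequence is limited.** The row is descriptive, is not among the AE summaries that protocol 10.6.2 lists, and feeds no test, stopping rule or primary outcome. Conceded.

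**A stronger reading is tempting.** From three hospitalisations a year a reader might infer that most patients would be barred from the table and that non-serious AEs would be understated several-fold. The documents do not support that. The figure is background on dialysis patients in general. Protocol 9.3.3 says that an admission does not always qualify as an AE; 9.4 keeps events typical of ESRD and dialysis out of AE reporting in general; 9.5.2 exempts documented prescheduled or elective admissions from SAE status; and the exclusions in 5.2, including the one on expected death within a year, select patients with a better outlook. Clustering of admissions lowers the share with any SAE further.

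**Conclusion.** The point holds as a defect in the definition of one descriptive table. Followed as written, the table understates non-serious AE incidence by term, and its overall line only restates the difference between two counts already planned. Neither result needs an assumed SAE rate.

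The size does need one. A factor of about 1.4 to 3 is reasonable for SAE proportions of 30% to two-thirds under independence. From the background admission rate, factors above 3 arise only if most or all admissions are SAEs and admissions are not strongly clustered; 8.5 is the extreme and not an expectation. A several-fold error is therefore possible but not established.

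The bias between arms is conditional too: it requires arms that differ in SAE rate and a broadly similar association between SAEs and non-serious AEs across arms. The primary safety outcome, major plus clinically relevant non-major bleeding, is not affected. The change should be made because it is almost free, but the flaw does not threaten the trial's main safety conclusion.

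**What to change.** In SAP 2.3.3, define the table as subjects with at least one non-serious TEAE, regardless of whether they also had an SAE, by system organ class and preferred term, with all safety-population patients in the arm as denominator.

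If the sponsor wants to keep the mutually exclusive category, label it as non-serious TEAEs only (no SAE) and show it beside the unrestricted table, so that neither is mistaken for the other.

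The cost is one definition line in the SAP and one filter in the table program. No new data are needed and no other analysis changes.
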